## **6. STUDY POPULATION**

Prospective approval of protocol deviations to recruitment and enrolment criteria, also known as protocol waivers or exemptions, is not permitted.

### **6.1. Inclusion Criteria**

Subjects are eligible to be included in the study only if all of the following criteria apply:

#### **Age**

1. Subject must be 65 to 80 years of age inclusive, at the time of signing the informed consent.

## Type of Subject and Disease Characteristics

2. Subjects with a diagnosis of ATTR-CM
  - a. Wild-type ATTR status must be confirmed by genotyping AND have one of the following:
    - i. Definite histochemical identification of amyloid by Congo red staining and green birefringence in crossed polarised light in cardiac or other tissue biopsy **and** identification of TTR as the amyloid fibril protein either by immunohistochemistry or proteomic analysis
  - OR**
  - ii. Scintigraphy Technetium-99m-labelled 3,3-diphosphono-1,2-propanodicarboxylic acid (99mTc-DPD) with confirmed myocardial uptake.
- b. Hereditary ATTR amyloidosis (e.g. TTR Val30Met) should have a known amyloidogenic TTR mutation demonstrated by genotyping AND is recognised to be primarily associated with cardiomyopathy AND one of the following:
  - i. Definite histochemical identification of amyloid by Congo red staining and green birefringence in crossed polarised light in cardiac or other tissue biopsy and identification of TTR as the amyloid fibril protein either by immunohistochemistry or proteomic analysis.

Note: Subjects with a confirmed mutation but who have not been biopsied may be eligible if they have an affected close blood relative whose amyloid has been confirmed histochemically. Such cases should be discussed with the Medical Monitor.

**OR**

- ii. Scintigraphy: 99mTc-DPD with confirmed myocardial uptake.

## Sex

3. Both male and female subjects are eligible to participate.

### a. Male subjects:

A male subject must agree to use contraception as detailed in [Appendix 5](#) of this protocol during the treatment period and for at least 3 months after the last scan and refrain from donating sperm during this period.

### b. Female subjects:

A female subject is eligible to participate if she is not of childbearing potential as defined in [Appendix 5](#).

## Informed Consent

4. Capable of giving signed informed consent as described in [Appendix 3](#) which includes compliance with the requirements and restrictions listed in the informed consent form (ICF) and in this protocol.

## Other

5. New York Heart Association (NYHA) up to class 3; subjects should be clinically stable for at least 3 months preceding to Screening.

## 6.2. Exclusion Criteria

Subjects are excluded from the study if any of the following criteria apply:

### Medical Conditions

1. Cardiomyopathy primarily caused by non-amyloid diseases (e.g. ischemic heart disease; valvular heart disease).
2. Interval from the Q wave on the ECG to point T using Fredericia's formula (QTcF) >500 msec.
3. Sustained (at a rate of  $\geq 120$  beats per min for  $\geq 30$  seconds), or symptomatic monomorphic ventricular tachycardia (VT), or rapid polymorphic VT, at screening/baseline cardiac monitoring.
4. Systolic blood pressure  $\leq 100$  mm/Hg based on triplicate readings at screening.
5. Unstable heart failure defined as emergency hospitalization for worsening, or decompensated heart failure, or syncopal episode within 1 month of screening.
6. Implantable cardiac defibrillator (ICD) or permanent pacemaker (PPM) at screening.
7. Estimated Glomerular filtration rate (eGFR) at Screening  $< 50$  mL/min calculated using modification of diet in renal disease (MDRD).
8. Any active and persistent dermatological condition, which in the opinion of the Investigator and Medical Monitor would preclude safe participation.
9. History of allogeneic stem cell transplantation, prior solid organ transplant, or anticipated to undergo solid organ transplantation, or left ventricular assist device (LVAD) implantation.
10. Malignancy within last 5 years, except for basal or squamous cell carcinoma of the skin, or carcinoma in situ of the cervix that has been successfully treated.  
*Note: Subjects with a history of other malignancies that have been curatively treated may be eligible, but must be discussed with and approved by the Medical Monitor.*
11. Acute coronary syndrome, or any form of coronary revascularization procedure (including coronary artery bypass grafting [CABG]), within 6 months of screening.
12. Symptomatic, clinically significant autonomic neuropathy which the Principal Investigator (PI) feels will preclude administration of study treatment.
13. Uncontrolled hypertension during Screening.

14. Alanine transaminase (ALT) >3x upper limit of normal (ULN) OR bilirubin >1.5xULN (isolated bilirubin >1.5xULN is acceptable if bilirubin is fractionated and direct bilirubin <35%).
15. Peripheral oedema at Screening that in the opinion of the PI or designee might prevent adequate absorption of subcutaneously administered CPHPC.
16. Presence of any co-morbid (e.g. steroid refractory rheumatoid arthritis), or an uncontrolled medical condition (e.g. diabetes mellitus), which in the opinion of the investigator would increase the potential risk to the subject. *Investigator should liaise with the Medical Monitor where there is uncertainty as to the eligibility of a patient.*
17. Positive test for hepatitis B, hepatitis C, and / or human immunodeficiency virus (HIV) during Screening, or within 3 months prior to first dose of study treatment.
18. Clinically significant multiple or severe drug allergies, intolerance to topical corticosteroids, or severe post-treatment hypersensitivity reactions (including, but not limited to, erythema multiforme major, linear immunoglobulin A [IgA] dermatosis, toxic epidermal necrolysis, and exfoliative dermatitis).
19. Inability to comprehend and / or understand the study patient information sheet, and / or unwillingness or inability to follow the procedures outlined in the protocol.

#### **ATTR-CM Specific Criteria**

20. Has any of the following:
  - a. Fulfilment of diagnostic criteria for AL amyloidosis
  - b. Fulfilment of diagnostic criteria for amyloid A (AA) or non-TTR hereditary amyloidosis
21. ATTR Disease Load:
  - c. Histologically proven or clinically suspected gastrointestinal TTR amyloidosis
  - d. Diffuse skeletal muscle uptake of 99m(Tc)-DPD on Single-photon emission computed tomography (SPECT) imaging (where available)
  - e. Peripheral neuropathy causing more than mild morbidity (e.g. walking disability; neuropathic pain affecting activities of daily living)
  - f. Proven or clinically suspected intracranial TTR involvement including ophthalmological disease
22. Non-amyloidosis related chronic liver disease (with the exception of Gilbert's syndrome or clinically asymptomatic gallstones)  
  
Note: Stable chronic liver disease should generally be defined by the absence of ascites, encephalopathy, coagulopathy, hypoalbuminaemia, oesophageal or gastric varices, or persistent jaundice

#### **Prior/Concomitant Therapy**

23. Participation in a separate clinical trial involving CPHPC within 3 months of screening

24. Any prohibited concomitant medication as per Section 7.7.2 within referenced timeframe

#### **Prior/Concurrent Clinical Study Experience**

25. Treatment with another investigational drug, biological agent, or device within 6 months of screening, or 5 half-lives of the study agent, whichever is longer.

#### **Diagnostic assessments for PET & Cardiac Magnetic Resonance (CMR) Scanning**

26. Orthopnoea of sufficient severity to preclude supine scanning as determined at screening
27. Inability to fit inside scanner due to body size (girth)
28. History of claustrophobia
29. Contraindication to MRI contrast agents
30. Contraindication for MRI scanning (as assessed by local MRI safety questionnaire), which includes but is not limited to:
  - a. Intracranial aneurysm clips (except Sugita) or other metallic objects
  - b. Intra-orbital metal fragments that have not been removed
  - c. Pacemakers or other implanted cardiac rhythm management/monitoring devices and non-MR conditional heart valves
  - d. Inner ear implants

#### **Other Exclusions**

31. Donation of blood or blood products in excess of 500 mL within 84 days of screening
32. Poor or unsuitable venous access

### **6.3. Lifestyle Restrictions**

The following restrictions apply:

#### **6.3.1. Caffeine, Alcohol, and Tobacco**

- Subjects will abstain from caffeine (e.g. tea, coffee, cola, chocolate) from Day 1 until final PET scan of dosing session, and 24 hours prior to any imaging scan.
- During each dosing session, subjects will abstain from alcohol for 24 hours prior to any imaging scan and for 24 hours prior to and during inpatient stays.
- Subjects who use tobacco products will be instructed that use of nicotine-containing products (including nicotine patches) will not be permitted 24 hours prior to any imaging scan or PK sample. Subjects will be required to adhere to clinical unit policy on tobacco/nicotine use.

### 6.3.2. Activity

Subjects will abstain from strenuous exercise for at least 24 hours before each blood collection for clinical laboratory tests. Subjects may participate in light recreational activities during studies (e.g., watching television, reading).

### 6.3.3. In-person Social Interaction

Following administration of  $^{89}\text{Zr}$ -GSK2398852, subjects will be advised to maintain a safe distance from young children and pregnant women consistent with local radiation safety guidelines. The clinical site should adhere to local hospital policy regarding in-person social interaction.

## 6.4. Screen Failures

Screen failures are defined as subjects who consent to participate in the clinical study but are not subsequently enrolled. A minimal set of screen failure information is required to ensure transparent reporting of screen failure subjects to meet the Consolidated Standards of Reporting Trials (CONSORT) publishing requirements and to respond to queries from regulatory authorities. Minimal information includes demography, screen failure details, eligibility criteria, and any SAEs.

Individuals who do not meet the criteria for participation in this study (screen failure) may be rescreened.

## 7. TREATMENTS

Study treatment is defined as any investigational treatments intended to be administered to a study subject according to the study protocol.

### 7.1. Treatments Administered

Study Treatment Name:	GSK2315698 (CPHPC)	GSK2398852 (unlabelled anti-SAP mAb)	$^{89}\text{Zr}$ -GSK2398852 ( $^{89}\text{Zr}$ -Df-labelled anti-SAP mAb)
Dosage formulation:	GSK2315698 Solution for Subcutaneous Injection or Intravenous Infusion, 200 mg/mL	GSK2398852 Concentrate for Solution for Infusion, 100 mg/mL	Solution containing 10 mg $^{89}\text{Zr}$ -GSK2398852 for Infusion, 10 mg/10mL or 10 mg/20mL

Study Treatment Name:	GSK2315698 (CPHPC)	GSK2398852 (unlabelled anti-SAP mAb)	Zr-GSK2398852 (Zr-Df-labelled anti-SAP mAb)
Unit dose strength(s)/ Dosage level(s):	200 mg/mL provided as 2 mL solution per vial Dosage levels: variable dependent on renal function	100 mg/mL provided as 1 mL solution per vial.  Variable total mass doses of anti-SAP mAb not exceeding 500 mg per dosing session	37 MBq  Zr-GSK2398852 associated with a mass of 10 mg GSK2398852
Route of Administration	Intravenous infusion usually for approximately 48 hours but up to 72 hours  Subcutaneous injection up to 3x daily for up to 8 days after unlabelled anti-SAP mAb dose per dosing session	Intravenous infusion of variable duration.	Refer to Table 6
Dosing instructions:	Study medication will be diluted in 0.9% w/v sodium chloride and administered by intravenous infusion by study personnel following specified regimens and by subcutaneous injection by study personnel in in-patient setting	Study medication will be diluted in 0.9% w/v sodium chloride and administered by intravenous infusion by study personnel following specified regimens	To be administered via separate intravenous cannula.  Refer to Table 6 See local Standard operating procedure (SOP) to protect from ionising radiation
Packaging and Labelling	Study Treatment will be provided in Type 1 clear glass vials sealed with grey polymer coated rubber stoppers that meet extractable criteria for sterile dosage forms. A silver aluminium overseal is placed over each vial and crimped. Each vial will be labelled as required per country requirement.	Study Treatment will be provided in glass vials. Each vial will be labelled as required per country requirement.	Study Treatment will be provided in glass vials. Each vial will be labelled as required per country requirement.

Study Treatment Name:	GSK2315698 (CPHPC)	GSK2398852 (unlabelled anti-SAP mAb)	Zr-GSK2398852 (Zr-Df-labelled anti-SAP mAb)
Manufacturer	Manufactured and supplied by GSK [0.9% w/v sodium chloride for dilution sourced locally by site]	Manufactured and supplied by GSK [0.9% w/v sodium chloride for dilution sourced locally by site]	VU University Medical Center Radiology & Nuclear Medicine

Anti-SAP mAb must not be administered until plasma SAP level has reached target. See Section 5.5.

See Section 5.4, Section 5.5, and Section 5.13 for additional dosing information.

## 7.2. Dose Modification

### 7.2.1. CPHPC dosing regimen according to renal function

**Table 8 CPHPC dosing regimen according to renal function**

Renal Function	IV dose level	SC dose regimen
eGFRa (mL/min/1.73 m^2)		
≥64	20 mg/hour	60 mg t.i.d
≥46 and < 64 b	10 mg/hour	60 mg t.i.d
<46	Consult Medical Monitor	Consult Medical Monitor

a. eGFR determined by MDRD (Modification of Diet in Renal Disease) must be used to define CPHPC dose based on renal function

b. Note renal withdrawal criteria in Section 8.1.3  
t.i.d. = three times daily, approximately 8 hours apart.

### 7.2.2. CPHPC Route of Administration Change

If the subject is unable to tolerate SC CPHPC injections post anti-SAP mAb infusion, in order to continue CPHPC, the investigator may switch the route of administration from SC injection to IV infusion. The Medical Monitor should be consulted in this instance.

## 7.3. Method of Treatment Assignment

Subjects will be identified by a unique subject number at screening that will remain consistent for the duration of the study. Upon completion of screening subjects will commence study treatments as described in Section 7. There will be no control group in this study.

The study has a non-randomised design. However, for internal study reporting, subjects will be assigned randomisation numbers for database/programming purposes, e.g. to flag screened subjects who commence study treatment and therefore are to be included in the All-Treated Population (see Section 10.3.1).

## 7.4. Blinding

This is a non-randomised open-label study. All investigators and GSK Study Team members, have direct access to the subject's individual study treatment and dosing schedules for each constituent drug.

Analyses for PET imaging data per subject will not be blinded.

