## 4. OBJECTIVES AND ENDPOINTS

Objectives	Endpoints
Primary	
Assessment of  Zr-GSK2398852 cardiac uptake as evaluated by PET imaging at different mass doses	Standardized Uptake Values (SUV) [i.e. Radioactivity concentrations] in focal anatomical locations within the heart, as well as SUV of the whole heart at different time points after  Zr-GSK2398852 administration and at different anti-SAP mAb TMDs.
Secondary	
Assessment of  Zr-GSK2398852 biodistribution in non-cardiac tissues and organs	Focal and total radioactivity uptake (including, but not limited to SUV) in different tissues

Objectives	Endpoints
	(including potentially at those peripheral tissue sites where transthyretin amyloidosis (TTR) amyloid deposition can be clinically occult) at different time points and after different TMDs.
Characterisation of the plasma pharmacokinetics of total mAb (unlabelled GSK2398852 and  Zr-GSK2398852)	Descriptive PK parameters, including the maximum concentration in plasma (C max ), the time associated with C max (T max ), clearance, terminal half-life (T 1/2 ) and the area under the concentration-time profile (AUC).
Characterisation of the plasma pharmacokinetics of radioactivity (  Zr-GSK2398852 radio-PK)	Descriptive PK parameters including the C max , T max , T 1/2 and AUC based on scintillation counter.
Safety & tolerability of Anti-SAP treatment including administration of  Zr-GSK2398852	All AEs including the incidence and grading of skin rashes, cardiac adverse events and infusion-related reactions, as well as other AEs utilizing standard pharmacovigilance practices.  Absolute changes in safety lab parameters, including cardiac troponin and NT-proBNP. Other safety information, including ECG, inpatient and outpatient cardiac telemetry, vital signs, and physical exam data.
Exploratory	
Correlation of regional pattern of  Zr-GSK2398852 uptake in the heart with the pattern of amyloid load by PiB scan and blood flow by WAT scan or MRI signal pattern	Maps of regional PET signals or MRI signals over the myocardium will be visually compared and scored.  Regional derived PET and MRI parameters correlated within and across ATTR-CM patients.

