#### Local tissue radioactivity concentration in organs in Regions of Interest (RoI)

##### SUVpeak:

A small sphere of 10-12 mm diameter placed in a representative location as seen in the image or transferred from the CT scan. Average of voxel (picture element) values within this volume is calculated.

SUVmean:

A larger outline of the whole organ or representative area or volume as seen in the image or transferred from the CT scan. Average voxel values (picture elements) within this volume is calculated.

Total organ radioactivity amount in Regions of Interest (RoI)SUVtotal\_organ:

An outline of the whole volume of the organ attempting to capture the total amount of radioactivity in that organ, as defined in the PET images or transferred from CT scan. Average of voxel (picture element) values within this volume is calculated.

VOLUMEtotal\_organ:

Corresponding total volume of the organs above

The SUVtotal\_organ and VOLUMEtotal\_organ are used for calculation of fraction of administered dose in that organ.

The organs/tissues of interest for analysis include:

Local tissue radioactivity concentration in organs in Regions of Interest (RoI)

Where relevant and depending on radioactivity uptake pattern:

- A minimum of 5 anatomical positions within the heart (only in the specific heart scans)
- Up to 3 focal and 1 larger location in each of the lungs
- Up to 3 focal and 1 larger location in the liver
- One focal and one large area in spleen
- One focal and one large area in pancreas
- One cortex and one medulla focal area in each of the kidneys
- One large area in the brain
- One large area in one thigh muscle
- Up to 5 small areas of the skin

Other focal or larger areas may be included depending on features in the images

For the regions in the 4\*5 scans focused over the heart, separate and average values will be generated for each of the RoIs.

Total organ radioactivity amount in Regions of Interest (RoI)

- Heart
- Liver
- Spleen
- One lung
- Both kidneys

Other organs may be included depending on features in the images

The PiB studies, performed only across the heart will be evaluated regionally and as “polar maps” using an extracted parameter called “retention index” which indicates the degree of retention as compared to washout.

The WAT studies will be evaluated regionally with automatic software which generates values and “polar maps” representing absolute blood flow values.

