12.4.4. Appendix 4A: Additional Endpoint Information

All the PET imaging variables are derived by the PET imaging centre and not the responsibility of S&P.

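### The reader who places the focal cardiac PET regions is not masked to the mass dose; masking that reader would be a cheap, though partial, safeguard

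*Protocol*

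**What the plan says.** - **Blinding.** Protocol 7.4 describes a non-randomised open-label study in which investigators and sponsor team members "have direct access to the subject's individual study treatment and dosing schedules for each constituent drug". It then adds, for image analysis: "Analyses for PET imaging data per subject will not be blinded". This is a stated choice, not an omission.
- **Primary endpoint.** Protocol 4 defines it as SUV "in focal anatomical locations within the heart, as well as SUV of the whole heart at different time points after" tracer administration, and at different TMDs. SAP 7.1.4 (Table 2) reports SUVmean for the whole heart and SUVpeak for each focal cardiac location.
- **How regions are set.** Protocol 10.3.7 (repeated in SAP 12.4.5) defines the SUVpeak region as "A small sphere of 10-12 mm diameter placed in a representative location as seen in the image or transferred from the CT scan". SUVmean uses "A larger outline of the whole organ or representative area or volume as seen in the image or transferred from the CT scan". Further detail is left to the Imaging Acquisition and Analysis Manual, which is not among the documents.
- **Which cardiac regions.** The cardiac PET listing shell in SAP Appendix 10 (PD_L1) has seven columns. Three are blood pools (left atrium, left ventricle, right ventricle). Four are wall regions named by intake: left ventricle wall high and low, and mid septum high and low.
- **Who derives the values.** SAP 12.4.4: "All the PET imaging variables are derived by the PET imaging centre".
- **What the values are used for.** SAP 3.1 names cardiac SUV and plasma radio-PK as the expected main parameters of the in-stream reviews that can change dose and scan timing. A cardiac/plasma ratio of at least 0.5 opens the optional evaluations in Protocol 10.3.3 and 10.3.4. Equivocal myocardial uptake throughout Part A is one ground for starting Part B (Protocol 5.2).

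Neither document describes a masked read, a second reader, a repeat read or a fixed placement rule.

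**The concern.** Open-label treatment does not require open-label image reading. The focal values depend on where a small sphere is placed, and nothing in the plan keeps the TMD from the person who places it.

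The risk is sharpest in Protocol 10.3.4. There the unlabelled dose is raised in session 2 to see whether the cardiac signal falls, and a fall is read as displacement from SAP on amyloid. A reader who knows that the second scan set belongs to the higher dose also knows which result supports specific binding. With at most six subjects, no control group and no repeat read, a placement effect in one subject could not be told apart from a dose effect. The same holds for a ratio close to 0.5, where a small change decides whether uptake is declared.

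**Working it through.** **1. The plan's own figure.** The sample size is 3 (Part A) + 3 (Part B) = 6, set by feasibility (Protocol 10.2). There is no hypothesis test, effect size or SD, so no power or error-rate calculation applies.

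**2. Can CT transfer remove the reader's choice?** The definition allows either the PET image or CT. CT shows anatomy, not tracer uptake. The three blood-pool regions could be set from CT. The four wall regions named by high or low intake cannot be set from CT alone, because someone must first judge intake on the PET image. Whole-heart SUVmean, an outline of the organ, leaves less room for choice.

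**3. Is the focal value sensitive to position?** Protocol 10.3.7.1 expects a tissue/plasma ratio of 0.1 to 0.2 from passive distribution and 0.5 in the blood pool. If a fraction *f* of the region lies in blood pool, and image blurring is ignored:

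ratio = (1 − *f*) × passive + *f* × blood pool

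- Passive 0.1: each 10% of blood pool adds 0.1 × (0.5 − 0.1) = 0.04, which is 40% of 0.1.
- Passive 0.2: each 10% adds 0.1 × (0.5 − 0.2) = 0.03, which is 15% of 0.2.
- Mixing alone reaches 0.5 only at *f* = 1. With an assumed hematocrit of 0.45 (blood-pool ratio 0.55), *f* must be 0.40/0.45 = 0.889 or 0.30/0.35 = 0.857. With 0.40 (ratio 0.60), it must be 0.40/0.50 = 0.80 or 0.30/0.40 = 0.75.

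So position can move a low focal value noticeably, but cannot by itself turn passive distribution into a positive call unless the region lies mostly or wholly in blood.

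**4. When could placement change the 0.5 call?** The plasma term is measured separately, so a proportional shift *s* in tissue SUV passes straight into the ratio. A shift up or down can change the call only for true ratios from 0.5/(1 + *s*) to 0.5/(1 − *s*). The documents give no value of *s*; these are assumptions.

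| Assumed shift *s* | Lower limit | Upper limit |
|---|---|---|
| 5% | 0.476 | 0.526 |
| 10% | 0.455 | 0.556 |
| 20% | 0.417 | 0.625 |
| 30% | 0.385 | 0.714 |

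**5. Does the reader need the TMD?** SUV is the measured radioactivity concentration, corrected for decay and normalised to administered activity per body weight (Protocol 10.3.7). The mass of unlabelled antibody does not enter. The radioactivity dose is planned to be the same in every session (Synopsis, Treatment Groups and Duration). Dose selection rests with the project team (Protocol 5.13.1), while the imaging centre derives the values. The two tasks can be separated.

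**6. Amount of work.** At the protocol's maximum numbers (5.2 and 5.13.2, scans counted per session):

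- Sessions: 3 × 2 + 3 × 1 = 9.
- Scans in Part A: 2 × 2 × 3 + 1 × 2 × 2 = 16. In Part B: 3 × 1 × 2 = 6. Total 22.
- Cardiac regions, at a minimum of 5 per scan: 22 × 5 = 110.

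**The case against.** The strongest reply is that the study is exploratory, tests nothing, and reports PET results as individual listings and plots without descriptive statistics (SAP 2.2, 7.1.2). Unblinded reading is openly declared. That stands and limits the severity. It does not make the point empty, because the same values steer dose, scan timing and the Part B decision.

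Second, the imaging manual may contain placement rules, and CT transfer is an equal option. Also true: how much discretion remains is unknown. But Section 7.4 governs blinding whatever the manual says, and the high and low intake regions still require a look at the PET signal.

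Third, masking would be incomplete. The first subject's session 1 TMD is printed in the protocol, scans arrive one session at a time, and slower tracer clearance at higher TMD (Protocol 5.13.1) may show in blood-pool intensity. This stands. Withholding the earlier session's region positions could also harm matched placement within a subject, so the remedy must not go that far.

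Some stronger readings are tempting but not supported:

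- *Visual scoring also threatens the primary endpoint.* The statement "Maps of regional PET signals or MRI signals over the myocardium will be visually compared and scored" describes an exploratory endpoint. SAP 2.2 drops the PiB and WAT scans and reduces the MRI comparison to an informal scatter plot.
- *The expected pattern is always known.* Protocol 5.12.1.2 and 5.13.1 describe opposing effects of mass dose. A clear direction exists only in the displacement evaluation, which is optional and follows a session 1 ratio of at least 0.5.
- *A percentage bias can be stated*, for example by assuming the highest of several positions at one dose and the lowest at another. No reader variability is given, and the shell lists high and low regions separately, so such a swap would mean mislabelling. What remains is smaller drift within each label.
- *Masking costs nothing.* No section costs it, and Protocol 10.3.2 calls programme decisions time critical.

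**Conclusion.** The point holds as a cheap improvement, not as an error in the plan. Focal cardiac SUVpeak depends on reader-chosen positions, the PET analysis is declared unblinded, and no other safeguard is stated. The exposure is concentrated in two places: the optional within-subject displacement comparison and ratios close to 0.5. Whole-heart SUVmean is less exposed.

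The size is unknown. The bands in the working show where a shift would matter; they do not say how large it is. The conclusion assumes that the reader may know the TMD (Section 7.4 imposes no masking but does not say what the imaging centre is told), that the unseen manual does not already fix the positions, and, for the 0.5 limit, that a focal wall value supplies the numerator.

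**What to change.** Amend Protocol 7.4, and carry the change into SAP 12.4.4 and 12.4.5, as follows:

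1. The imaging-centre reader is not told the TMD or the sponsor's dose expectations when placing cardiac regions.
2. Cardiac regions and their SUVs are saved and locked before they are linked to TMD for each in-stream review.
3. For a subject's second session, the reader may have the region positions from the first, without the SUV values, so that locations are matched.
4. All other staff stay open-label.

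No extra reader is needed, and dose selection proceeds as planned. The cost is the removal of dose information from what the reader receives and a short lock step before each review, over at most 9 sessions and 22 scans. The masking would be partial, for the reasons given above, and the study report should say so.
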